7.2. Study Risk Assessment

The devices utilized in this study do not meet the definition of an SR device under 21 CFR 812.3(m) included in device Section 5.1. Therefore, this study can be classified as a Non-Significant Risk device study.

7.3. Adverse Events

7.3.1. Adverse Event Definitions

Adverse Event (AE)

Any untoward medical occurrence in a clinical investigation participant which does not necessarily have to have a causal relationship with the study procedures.

An AE can therefore be any clinically significant sign (including an abnormal laboratory finding, for example), symptom, or disease temporally associated with the study procedures, whether or not considered related to the study procedures.

Any abnormal laboratory findings, abnormal safety assessments, or anticipated day-to-day fluctuations which are associated with a pre-existing disease or condition, are not considered an AE, unless judged by the investigator to be worsening or more severe than expected.

Serious Adverse Event (SAE)

A serious adverse event (SAE) is defined as any AE that is fatal, life-threatening, results in persistent or significant disability, requires medical or surgical intervention to prevent permanent impairment or damage, or results in hospitalization.

Any SAE, including death, due to any cause (related or unrelated to the study or a study device) will be documented on the AE form and will be reported immediately (within 24 hours of learning of the event) by Study Staff to the Sponsor.

7.3.2. Categorization of Adverse Events

The severity of an AE will be categorized as follows:

Mild:	The event is transient, easily tolerated by the participant, and does not affect the participant's daily activities.
Moderate:	The event causes the participant discomfort and interrupts the participant's usual daily activities. May require treatment but not extended hospitalization for the participant.
Severe:	The event is incapacitating, causing inability to do work or usual activities; signs and symptoms may require medical evaluation and/or treatment, and may require additional prolonged hospitalization.

7.3.3. Causal Relationship Assessment

The assessment of causal relationship to study procedures is required for the purposes of reporting AEs. When determining the relationship of study procedures to an AE, to promote consistency, the following guidelines should be taken into consideration, along with good clinical and scientific judgment:

The relationship of each AE to study procedure(s) will be assessed using the following categories:

Probably Related:	There is a strong temporal relationship to the study or device, and an alternative etiology for the AE is unlikely.
Possibly Related:	The event is not readily explained by the participant's medical condition, concomitant therapy, or other causes, and there is a plausible temporal relationship between the event and participation in study procedures.
Probably Not Related:	An event for which an alternative explanation is more likely (e.g., concomitant medications or ongoing medical conditions) or the temporal relationship to study procedures and/or exposure suggests that a causal relationship is unlikely.
Not Related:	An AE that does not follow a reasonable temporal sequence from participating in study procedures and/or that can reasonably be explained by other factors, such as underlying diseases, complications, concomitant drugs, and concurrent treatments.

7.3.4. Anticipated Adverse Device Effects

There are no Anticipated Adverse Device Effects from the provided smartphone or wireless headphones.

The following occurrences are not to be regarded as AEs:

- Hearing symptoms or diseases (including tinnitus)
- Cerumen impaction
- Abnormal audiogram findings
- Complaint about smartphone or comfort of headphones
- Discomfort or injury with ear exams and/or with removal of ear wax
- Study app functionality issues

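### Protocol 7.3.4 takes on-study hearing symptoms, tinnitus and ear-procedure injury out of adverse-event status, in conflict with 7.3.1; applied as written, the AE tables cannot speak to these events

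*Protocol*

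**What the plan says.** Protocol 7.3.1 defines an adverse event broadly: "Any untoward medical occurrence in a clinical investigation participant which does not necessarily have to have a causal relationship with the study procedures". It then takes out laboratory findings, safety assessments and expected daily fluctuations tied to a condition the participant already had, but brings them back with the words "unless judged by the investigator to be worsening or more severe than expected". Seriousness is built on the same base: "A serious adverse event (SAE) is defined as any AE that is fatal, life-threatening", followed by the other seriousness criteria.

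Protocol 7.3.4 introduces a list with "The following occurrences are not to be regarded as AEs". Its six items include "Hearing symptoms or diseases (including tinnitus" (the bracket closes there in the source), "Abnormal audiogram findings", "Discomfort or injury with ear exams and/or with removal of ear wax" and "Cerumen impaction". The other two are complaints about the phone or headphone comfort, and app faults. No item is limited by time of onset, change from baseline, or seriousness.

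Elsewhere, Protocol 7.1 names perforation of the eardrum and laceration of the canal among the risks of wax removal. Protocol 4.8 and 7.5 foresee tinnitus arising during participation and allow withdrawal for it. Protocol 7.4.1 sends AEs to the AE form. SAP 9.8 and Tables 14.3.1.1 to 14.3.1.5 summarise AEs, and neither mentions the 7.3.4 list.

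**The concern.** The device sits in the ear and amplifies sound, and the study includes ear examinations with possible wax removal. New or worsening hearing symptoms, tinnitus and procedural injury are therefore among the events a reader of the safety section would look for first. The list in 7.3.4 removes them by definition.

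Leaving out the hearing loss that participants bring with them is sensible, since AE recording starts at consent and the population is selected for hearing difficulty. The trouble is that the wording does not stop there. It also covers what arises or worsens on study, and it covers injury, which is not a baseline condition. If a table then shows few or no such events, the reader cannot tell whether they did not occur or were not counted.

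**Working it through.** There is no figure to reproduce, so the check sets the sections side by side and follows an event from occurrence to table.

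| Step | New tinnitus on study | Pre-existing hearing problem that worsens | Eardrum perforated at wax removal |
|---|---|---|---|
| Protocol 7.3.1 | AE under the general definition | AE under the general definition; where the exemption for pre-existing conditions applies, the worsening clause restores it | AE under the general definition; the worsening clause is not relevant |
| Protocol 7.3.4 | Not an AE | Not an AE | Not an AE |
| SAE status under 7.3.4 | None, because an SAE must be an AE | None | None |
| AE form (Protocol 7.4.1) | Not required | Not required | Not required |
| SAP Tables 14.3.1.1 to 14.3.1.5 | No entry | No entry | No entry |

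The nature of the conflict therefore differs by item. For hearing symptoms, 7.3.4 contradicts the general definition and, where a pre-existing condition is involved, is also out of step with the worsening exception. For procedural injury, the contradiction is with the general definition alone.

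Next, does any other text bring the events back?

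- The 7.3.1 instruction to report every SAE whatever its cause does not, because the event must first be an AE.
- The unanticipated adverse device effect definition (Protocol 7.3.5) does not depend on AE status, so a serious hearing event caused by the device might qualify. It is limited to serious effects not already identified in the study documents. A wax-removal perforation is procedural and already named in 7.1, so it would not appear to qualify. The SAP lists no table for these effects.
- Withdrawal reasons are tabulated (SAP 9.1). A participant withdrawn for tinnitus would leave a trace there, for example under investigator discretion, but not as an AE. Anyone who stays in the study leaves none by this route.
- Protocol 10.3 requires new safety information to go to the IRB. That is notification, not tabulation.

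Last, which items matter in practice? Pure tone audiometry is possible at screening and done at Clinic Visit 1 (Protocol 3.2 and 8.1.4.4). None is scheduled after device use, so the audiogram item has little effect. Of the six items, the two on hearing symptoms and procedural injury carry the point.

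**The case against.** The strongest reply is that a specific list narrowing a general definition is an ordinary drafting choice. Without some such list, baseline hearing findings in this population could be logged as AEs from the day of consent. SAPs also commonly rely on the protocol for definitions, and SAP 9.8 does not restate the AE and SAE definitions either. This stands as a reason to keep a list. It does not explain why the list extends to new symptoms and to injury, and no text says that 7.3.4 overrides 7.3.1.

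Several stronger readings are tempting, and the documents do not support them.

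- A reader might infer that the worsening clause condemns the whole list. It concerns findings tied to pre-existing conditions and says nothing about procedural injury.
- A reader might infer that sites will count differently. Nothing shows sites applying different sections, and AE-form instructions are not among the documents.
- A reader might size the gap by the number of planned ear examinations or hours of wear. Those are denominators; without an event rate they give no effect.
- A reader might say that the AE tables are the only tabulated safety information. Withdrawal reasons are tabulated too.
- A reader might infer that every ear problem is lost. Otitis and injury from headphone wear are not plainly on the list, so they arguably remain AEs under 7.3.1.

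**Conclusion.** The point holds for two kinds of event: hearing symptoms or tinnitus that are new or worsen on study, and injury from ear examination or wax removal. Under 7.3.4 as written, these have no route to the AE form, to SAE status under the 7.3.1 wording, or to any of the five planned AE tables. A low or zero count could not then support a safety statement about them.

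The conclusion assumes that 7.3.4 is applied literally. If 7.3.1 were followed instead, such events would be captured, but the plan does not say so. The documents give no event rates, so the number of events affected is unknown and could be small.

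The defect is in recording and tabulation. It does not show that participants would go without care: Protocol 7.1 encourages them to report injuries, and 7.5 assigns management of complications. The primary IOI-HA analysis is unaffected. This should be corrected, but it does not undermine the trial's main conclusion.

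**What to change.** Reconcile Protocol 7.3.1 and 7.3.4.

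- Limit the list of non-AEs to hearing or audiogram findings that were present at entry and have not changed, impacted wax without injury, comfort complaints without injury, and app issues.
- Record new or worsening hearing symptoms or tinnitus, and any injury from ear examination or wax removal, on the existing AE form.
- Tabulate these events by arm in the existing Tables 14.3.1.1 to 14.3.1.5.
- State the revised list in SAP 9.8, so that a reader of the tables can see what they leave out.

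The cost is a wording amendment to the protocol, which Protocol 10.3 sends to the IRB, and a matching statement in the SAP. The form and tables already exist. AE counts will be somewhat higher. Whether a symptom has worsened becomes an investigator judgement in a trial where participants know their arm, and with no audiogram scheduled after device use, that judgement will rest largely on what participants report.

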7.1. Anticipated Risks to Participants

Participants may have risks or discomforts while in this study. Precautions will be taken to minimize risks, and the participant will be encouraged to talk to the Study Staff if he/she experiences any injuries, side effects, or discomfort during this study.

Potential risks and discomforts may include:

- **Previously unknown hearing loss:** Participants may experience symptoms of stress and anxiety related to objective finding of hearing loss. They will have access to the study Audiologist who can address frequently asked questions.
- **Discomfort or injury with ear exam and ear wax removal:** Clinic visits include examination of the ears by an audiologist who may remove ear wax if deemed required and consented to by participant. Some participants may experience discomfort with ear exams. Removal of ear wax is

common in audiology practices and considered safe but does have potential risks of eardrum perforation, a laceration in the ear canal, dizziness, and/or inability to remove ear wax.

- **Discomfort with headphone wear:** Some participants may find it uncomfortable to wear the wireless headphones in *Home Interval 1* and in *Home Interval 2*. If comfort prohibits a participant from this wireless headphone wear, they will be withdrawn from the study.
- **Loss of confidentiality due to study data breach:** To minimize this risk, the Study Staff will adhere to rigorous standards to protect the data. All data collected from participants will be coded and separated from any directly identifiable information (DII). Although the Study Staff will take precautions to protect the participant's identity, such as keeping study records in a secure location with restricted access and removing information traditionally used to identify participants when their study data is shared, we cannot guarantee that their identity will never become known to the Study Sponsor. It is possible that there could be unauthorized access to, or security breaches of, the systems used to store information, and there may be other privacy risks that are not foreseen.
- **Loss of confidentiality related to storing health data on an app:** Participants will be reminded not to share their mobile device login information with others and receive training on best practices on preventing the infiltration of DII into the study app. Only the Study Staff will have access to the primary study crosswalk.

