- Not Related: An AE that does not follow a reasonable temporal sequence from participating in study procedures and/or that can reasonably be explained by other factors, such as underlying diseases, complications, concomitant drugs, and concurrent treatments.

Study procedure related events will include those events classified as possibly or probably related to the study procedure.

Action taken will be defined as:

- None;
- Study procedures interrupted;
- Study procedures stopped

Outcome will be defined as:

- Resolved;
- Ongoing or stabilized and followed by private healthcare provider;
- Lost to follow up

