Table 14.2.1.3	Logistic Regression Analysis to Evaluate Probability of Missingness – Per Protocol Analysis Set
Table 14.2.1.4	Primary Endpoint Analysis of IOI-HA – Per Protocol Analysis Set
Table 14.2.1.5	Primary Endpoint Analysis of IOI-HA – Complete Cases Analysis Set
Table 14.2.1.6	IOI-HA Item Summary – Complete Cases Analysis Set
Table 14.2.2	QuickSIN Results– Complete Cases Analysis Set
Table 14.2.3.1.1	Real Ear Measures Summary at 50 dB SPL (Clinic Visit 2) – Complete Cases Analysis Set
Table 14.2.3.1.2	Real Ear Measures Summary at 50 dB SPL (Clinic Visit 3) – Complete Cases Analysis Set
Table 14.2.3.2.1	Real Ear Measures Summary at 65 dB SPL (Clinic Visit 2)– Complete Cases Analysis Set
Table 14.2.3.2.2	Real Ear Measures Summary at 65 dB SPL (Clinic Visit 3)– Complete Cases Analysis Set
Table 14.2.3.3.1	Real Ear Measures Summary at 80 dB SPL (Clinic Visit 2) – Complete Cases Analysis Set
Table 14.2.3.3.2	Real Ear Measures Summary at 80 dB SPL (Clinic Visit 3) – Complete Cases Analysis Set
Table 14.2.4.1	Mean Absolute Difference of Real Ear Measures from NAL-NL2 Targets at 50 dB SPL– Complete Cases Analysis Set
Table 14.2.4.2	Mean Absolute Difference of Real Ear Measures from NAL-NL2 Targets at 65 dB SPL
Table 14.2.4.3	Mean Absolute Difference of Real Ear Measures from NAL-NL2 Targets at 80 dB SPL

Table 14.3.1.1	Summary of Adverse Events – Full Analysis Set
Table 14.3.1.2	All Adverse Events Sorted Alphabetically – Full Analysis Set
Table 14.3.1.3	Serious Adverse Events – Full Analysis Set
Table 14.3.1.4	Adverse Events Possibly or Probably Related to Study Procedures – Full Analysis Set
Table 14.3.1.5	Adverse Events Rated Severe in Intensity – Full Analysis Set

List of Listings

Listing 16.2.1	Discontinued Patients
Listing 16.2.2.1	Protocol Deviations: Type and Description
Listing 16.2.2.2	Protocol Deviations: Severity and Actions Taken
Listing 16.2.4.1	Baseline Demographics
Listing 16.2.6.1	IOI-HA Responses
Listing 16.2.7.1	Adverse Events: Description and Timing
Listing 16.2.7.2	Adverse Events: Severity and Relationship
Listing 16.2.7.3	Adverse Events: Actions and Outcomes
Listing 16.2.9.1	Subject Eligibility and Enrollment
Listing 16.2.9.2	Perceived Hearing Loss Questionnaire
Listing 16.2.9.3	Subject Disposition
Listing 16.2.9.4	Medical History
Listing 16.2.9.5.1	Otoscopy Examination Results
Listing 16.2.9.5.2	Otoscopy Examination Additional Information
Listing 16.2.9.6	Clinical Visits Summary
Listing 16.2.9.7.1	Pure Tone Reference Audiometry (1)

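### Protocol 7.3.4 says injury from ear exams or wax removal is not an adverse event, so a zero in the procedure-related AE table would not show that no such injury occurred

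*Protocol*

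**What the plan says.** Under Protocol 3.2 an audiologist examines the ears at Clinic Visits 1, 2 and 3 and may remove wax each time, where needed and with consent. Protocol 7.1 calls removal common and considered safe, but adds that it "does have potential risks of eardrum perforation, a laceration in the ear canal, dizziness, and/or inability to remove ear wax".

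Protocol 7.3.1 defines an AE broadly, as an untoward medical event whether or not the study procedures caused it: "An AE can therefore be any clinically significant sign", symptom or disease. It then builds the serious category on top: "A serious adverse event (SAE) is defined as any AE that is fatal, life-threatening", with further criteria that include an event that "requires medical or surgical intervention to prevent permanent impairment or damage".

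Protocol 7.3.4 carves out exceptions. Its list opens "The following occurrences are not to be regarded as AEs", and one entry is "Discomfort or injury with ear exams and/or with removal of ear wax".

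SAP 9.8 summarises four groups: all AEs, SAEs, procedure-related AEs and severe AEs. On the third it says: "Study procedure related events will include those events classified as possibly or probably related to the study procedure". The table list in SAP 13 titles Table 14.3.1.4 "Adverse Events Possibly or Probably Related to Study Procedures". Table 14.3.1.3 holds the SAEs. The visible SAP text neither repeats nor overrides the Protocol 7.3.4 list.

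**The concern.** The plan names specific injuries as risks of a study procedure, then takes injury from that procedure out of the category on which all its safety tables are built. The entry treats passing discomfort and a perforated eardrum alike.

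At stake is what the safety report can be taken to mean. A reader who sees no events in the procedure-related table will conclude that the procedures did no recorded harm. For ear exams and wax removal, the table would not support that conclusion. AE or SAE status also triggers notification and follow-up, so the entry affects conduct as well as tabulation.

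**Working it through.** No arithmetic applies. The check follows one hypothetical event through the text: an eardrum perforated during wax removal at Clinic Visit 2 that needs medical or surgical intervention.

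1. **Is it on the exclusion list?** Yes. The Protocol 7.3.4 entry names injury, covers wax removal, and sets no limit by severity or seriousness.
2. **Is it an AE?** The general definition in Protocol 7.3.1 says yes. The specific entry in 7.3.4 says no. Under the usual reading, in which a specific exclusion governs a general definition, it is not an AE.
3. **Is it an SAE?** It meets a seriousness criterion. But 7.3.1 requires an SAE to be an AE first, and step 2 removed that status. The rule in 7.3.1 that SAEs of any cause go on the AE form applies only to events already classed as SAEs.
4. **Is it an unanticipated adverse device effect?** No. Protocol 7.3.5 covers serious effects tied to the device and not previously identified. This injury comes from a procedure, and 7.1 already identifies it.
5. **Which tables would hold it?** Tables 14.3.1.1 to 14.3.1.5 all count AEs or subsets of them. Relatedness under SAP 9.8 is assessed for AEs, so an event outside that class never reaches the procedure-related table.
6. **Which timelines apply?** Site reporting to the sponsor within 10 working days (Protocol 7.4.1), SAE reporting to the sponsor within 24 hours and to the IRB within 10 working days (7.4.2), and follow-up to resolution (7.4.4) all depend on AE or SAE status. Read literally, none is triggered.
7. **Could it leave another trace?** If the participant withdrew, the withdrawal would appear in subject accountability (SAP 9.1). That counts people who leave, not injuries. Clinical management under Protocol 7.5 does not depend on the AE label.

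Now take a second site that applies 7.3.1 and records the same event as an AE and SAE. Both sites can point to protocol text. The table entry then depends on which section the site followed.

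**The case against.** The strongest reply is that other text is wide enough to catch a real injury. Protocol 7.3.1 defines AEs broadly. Protocol 7.4.1 has staff evaluate participants at each visit and record all AEs, including those that staff observe. Protocol 7.5 collects AE information at every time point. A sensible investigator might well report a perforation. This stands in part: a reader might infer that no such injury could ever reach the tables, and the documents do not support anything so absolute. But each of these provisions applies to AEs, and none says that it prevails over the 7.3.4 list. They show a conflict, which supports clarifying the text.

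The second reply is about relevance. Wax removal is neither the device nor the randomized intervention. It is open to both arms, only when needed and consented to, and safety is not a stated objective. This stands and limits the weight of the point. It does not remove it, because the plan chose to report procedure-related events and this is a procedure whose risks it spells out. Dizziness, also named in 7.1, is not clearly an injury and may already count as an AE.

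A reader might also infer that the Visit 2 and 3 ear exams go unrecorded. Protocol 8.1.4.1 and SAP 9.4.1 do mention otoscopy at screening only. But Protocol 8.1.3 lists ear exam findings among the data that may be collected without naming a visit. Listings 16.2.9.5.1 and 16.2.9.5.2 are not limited to screening, and the case report forms and assessment figure are not available. Clinically significant findings outside the 7.3.4 list can already be AEs. Silence in incomplete documents does not establish that gap.

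**Conclusion.** The point holds as a defect in the AE definition that carries through to the safety tables. Following the plan as written leaves injuries from ear exams or wax removal out of Table 14.3.1.4 and, read literally, out of Table 14.3.1.3 and expedited reporting. An empty procedure-related table would be compatible with perforations or lacerations having occurred.

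Its size cannot be given in events, because the documents state no rate of wax removal or of injury, and none is assumed here. The opportunity arises at all three clinic visits, but permission to remove wax is not a count of removals. The primary IOI-HA comparison is untouched, and nothing suggests that an injured participant would go untreated.

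The conclusion rests on two assumptions: that the specific 7.3.4 entry prevails over the general 7.3.1 definition, and that no unseen study document, such as case report form instructions, overrides it. If the first fails at some sites, the result is inconsistent reporting, which the same change cures. It should be corrected.

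**What to change.** Delete *or injury* from the Protocol 7.3.4 entry and leave discomfort on the list. Injuries from ear exams and wax removal are then recorded as AEs and, where criteria are met, as SAEs. They reach the existing tables and timelines with no change to the SAP.

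If the sponsor prefers to keep the list, two additions are needed: a sentence in the Protocol that an injury meeting a seriousness criterion is still an SAE, and a separate tabulation in SAP 9.8 of all injuries from ear exams or wax removal.

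The first option costs one wording change and possibly a few more reported AEs. The second costs one Protocol sentence and one table. Neither adds a visit or alters the primary analysis.
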